10.5.2 Diet and Fluid Restrictions

10.5.2.1 Mealtimes/Fasts

Participants should be fasted 4 hours fast prior to their screening visit. There are no meal restrictions and no fasts required during the clinical conduct of the study.

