- Vital signs: Pre-dose and 30 mins (\pm 5 min) post dose
- Urine pregnancy test: Pre-dose
- Urine drugs of abuse (DOA) including alcohol and cotinine: Pre-dose
- Review of participant eligibility: Pre-dose
- Pharmacodynamic (PD) blood sample (antibody response): Pre-dose
- Exploratory blood sample (███████████): Pre-dose
- Administration of investigational vaccine
- Assessment of injection site: Pre-dose and 30 min (\pm 5 min) post-dose. Photographs may be taken of injection site reactions, as required
- Adverse event (AE) check
- Concomitant medication check
- Participants receive Participant Diary Card Day 1 to Day 7 to record temperatures, injection site reactions, general reactions, AEs and concomitant medication check from the evening of Day 1 to the evening of Day 7.

Visit 3 (Day 8 \pm 1 days), Visit 4 (Day 29 \pm 2 days), Visit 5 (Day 57 \pm 2 days) and Visit 6 (Day 85 \pm 5 days):

The following procedures will be performed:

- Vital signs
- Laboratory safety tests (biochemistry and haematology): Visit 3 (Day 8), Visit 4 (Day 29) & Visit 5 (Day 57)

- Brief physical examination: Visit 3 (Day 8) & Visit 4 (Day 29)* may also be performed at any other time point as clinically indicated
- PD blood sample (antibody response)
- Exploratory blood sample (███████████): Visit 3 (Day 8) only
- Assessment of injection site: Photographs may be taken of injection site reactions, as required.
- AE check
- Concomitant medication check
- Blood samples for future validation and calibration work will be collected on Day 29, Day 57 and Day 85
- Review of Participant Diary Card Day 1 to Day 7
- Participants receive Participant Diary Card Day 85 to Day 183 to record AEs and concomitant medication

Visit 7: Post Study Follow-Up (Day 183 ±7 days):

A post study follow-up visit will take place on Day 183 (±7 days) to ensure the ongoing wellbeing of the participants. The following procedures will be performed:

- Physical examination (brief)
- Vital signs
- Laboratory safety tests (biochemistry, haematology)
- Urinalysis
- Urine pregnancy test
- PD blood sample (antibody response)
- AE check
- Concomitant medication check
- Review of Participant Diary Card Day 85 to Day 183

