10.7.1.4.2 Laboratory Safety Assessments

Laboratory safety screen samples will be analysed by Simbec-Orion Laboratory Services or at an appropriate referral laboratory. Printed laboratory test result reports will include normal reference ranges. A decision regarding whether the laboratory test result outside the normal reference range is of clinical significance or not shall be made by an Investigator/designee and the report will be annotated accordingly. Clinically significant laboratory test result abnormalities will be recorded on the AE page. The normal reference ranges for laboratory test parameters will be detailed in the SLPDoc0024 Normal Reference Ranges and Alert Reference Values document.

Biochemistry Tests: Sodium, potassium, chloride, bicarbonate, blood urea, creatinine, creatine kinase, glucose, calcium, albumin, cholesterol, C- reactive protein (CRP), triglycerides, phosphorus (inorganic phosphate), lactate dehydrogenase (LDH), total protein, globulin, uric acid, alkaline phosphatase (ALP), aspartate aminotransferase (AST), alanine aminotransferase (ALT), gamma glutamyl transferase (GGT), total bilirubin and direct bilirubin.

Blood samples for biochemistry analyses for each time-point will be collected into an appropriately sized serum collection tube with or without a separator, and analysed by Simbec-Orion Laboratory Services, or at an appropriate referral laboratory, using an appropriate analyser/method(s) of analyses. Assessments of blood sample quality (i.e., for sample verification) will be performed by measuring 3 indices [namely, Lipaemic (for Lipaemia), Haemolytic (for Haemolysis) and Icteric (for Icterus)] in serum.

Haematology Tests: Red blood cell (erythrocyte) count, haemoglobin, HCT, platelet count, white blood cell (leukocytes) count with absolute differential (neutrophils, lymphocytes, monocytes, eosinophils, basophils which are reported in absolute and percentage values).

Blood samples for haematology analyses for each time-point will be collected into an appropriately sized blood collection tube containing ethylenediaminetetraacetic acid (EDTA)

and analysed by Simbec-Orion Laboratory Services, or at an appropriate referral laboratory, using an appropriate analyser/method(s) of analyses.

Urinalysis Tests: Specific gravity, pH, protein, glucose, ketones, occult blood, leukocyte esterase, nitrites.

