10.9.2 Study Variables/Endpoints

Primary Endpoints

- The following endpoints will be evaluated to assess the safety over 12 weeks of a single dose (booster or first dose) of the GBS vaccine (GBS-NN/NN2): local and systemic reactogenicity; AEs; laboratory tests; urinalysis; vital signs; physical examination.

Secondary Endpoints

- The following secondary **safety endpoints** will be evaluated to assess the long-term safety profile of the GBS-NN/NN2 vaccine 6 months following the dose (booster or first dose): the incidence of autoimmune diseases and/or clinically relevant medical events related to the vaccination that occur in the 6-month follow-up period.
- The following secondary immunological endpoints will be evaluated.

- Individual participant antibody concentration specific for GBS-NN and GBS-NN2, in µg/mL, at 0 and 84 days after the dose (booster or first dose).
- Individual participant antibody concentration specific for AlpCN, RibN, Alp1N and Alp2-3N, in µg/mL, at 0, 14, 28, 56, 84 and 182 days after the dose (booster or first dose).

From the endpoints listed above the following will be derived:

- Geometric mean fold increase in antibody concentration, specific for GBS-NN and GBS-NN2, between Day 1 and Day 85.
- Geometric mean fold increase in antibody concentration, specific for AlpCN, RibN, Alp1N and Alp2-3N, between Day 1 and Days 8, 29, 57, 85 and 183.
- Proportion of participants achieving antibody concentrations, specific for AlpCN, RibN, Alp1N and Alp2-3N, above 0.5, 1, 2, 4 µg/mL, 7, 28, 56, 84 and 182 days after receiving the dose (booster or first dose).

The secondary endpoints relating to antibody concentrations specific for AlpCN, RibN, Alp1N and Alp2-3N and all exploratory endpoints will be analysed and reported separately. Full details of the analyses will be documented in a separate plan(s).

The values of these endpoints on Day 85 will be the basis of the primary immunological analysis; this timepoint is anticipated to be the time of delivery after vaccination in a pregnant woman.

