Additionally, the above listings and summaries will be presented separately for autoimmune diseases and/or clinically relevant medical events related to the vaccination that occur in the 6-month (182 days) follow-up period, and systemic and local reactogenicity TEAEs (as defined in the SAP) occurring up to and including Day 85.

Physical examination: Physical examination results will be listed.

Laboratory Safety: Biochemistry, haematology, and urinalysis parameters will be listed with any out of normal range values flagged. Laboratory test results which are out of normal range will also be presented separately along with normal reference ranges. Descriptive statistics (N, n, mean, SD, minimum, median and maximum) of absolute and change from baseline (Screening) biochemistry and haematology parameters at each time point up to and including Day 85 will be tabulated.

Vital Signs: Vital signs parameters will be listed with any out of normal range values flagged. Descriptive statistics (N, n, mean, SD, minimum, median and maximum) of absolute and change from baseline (Day 1 pre-dose) values at each time-point will be tabulated.

Injection Site Reactions: A summary of injection site reactions will be produced by visit and category (redness, bruising, induration, itching and pain), including the number and percentage of participants in each category.

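### Biochemistry baseline is a fasted Screening sample but feeding state is not standardised after dosing, so within-group change in glucose and triglycerides at Days 8, 29 and 57 can be biased

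*Protocol*

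**What the plan says.** Protocol 10.5.2.1 sets two rules. For the first visit: "Participants should be fasted 4 hours fast prior to their screening visit". For the rest of the study: "There are no meal restrictions and no fasts required during the clinical conduct of the study".

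Protocol 10.9.4.3 plans descriptive statistics for laboratory data, including "change from baseline (Screening) biochemistry and haematology parameters at each time point up to and including Day 85 will be tabulated". In the same section the baseline for vital signs is the Day 1 pre-dose value.

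The biochemistry panel in 10.7.1.4.2 includes "creatinine, creatine kinase, glucose, calcium, albumin, cholesterol, C- reactive protein (CRP), triglycerides". The primary endpoints in 10.9.2 are "local and systemic reactogenicity; AEs; laboratory tests; urinalysis; vital signs; physical examination".

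The flow chart (Table 10.7.1) and the blood volume table (Table 10.7.2) place biochemistry at Screening, Days 8, 29 and 57, and the post-study visit on Day 183. Neither shows a laboratory sample on Day 1 or Day 85.

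**The concern.** A change from baseline can be read as an effect of dosing only if the two samples were taken under like conditions. Here the protocol fixes the condition for the baseline sample and leaves it open for every later one. For analytes that respond to a recent meal, the tabulated change then mixes food with anything the vaccine does.

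Laboratory tests belong to the primary safety endpoints, and every participant is vaccinated (10.6.9). No unvaccinated arm would show the same food shift without the vaccine. A reader of the tables could take a rise in mean glucose or triglycerides after dosing for a vaccine signal, or could dismiss a real one as food. The analysis plan cannot repair this later if feeding state was never collected.

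**Working it through.** The plan states no figure to reproduce on this point. The check sets the sections side by side and then adds an illustration on stated assumptions.

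**Cross-reading**

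| Step | Source | Finding |
|---|---|---|
| Condition at Screening | 10.5.2.1 | 4-hour fast |
| Condition after dosing | 10.5.2.1 | No fast required; feeding state open |
| Laboratory baseline | 10.9.4.3 | Screening |
| Alternative baseline | Tables 10.7.1 and 10.7.2 | None; no Day 1 laboratory sample |
| Visits in the change table | Table 10.7.1 with 10.9.4.3 | Days 8, 29 and 57 (no sample on Day 85; Day 183 lies beyond the table) |
| Meal-sensitive tests | 10.7.1.4.2 | Glucose and triglycerides, 2 of 24 listed |
| Recording of feeding state | Whole protocol | Not called for |

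Fasting is thus fixed at baseline and uncontrolled at follow-up, and nothing in the protocol separates its effect from that of vaccination within a group.

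**Illustration (assumptions, not documented values)**

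Let *f* be the share of post-dose samples drawn from women who have eaten recently. Let *d* be the fed-minus-fasted difference in units of the SD of the change.

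- Expected artefact in mean change = *f* × *d*.
- Chance that a 95% confidence interval for mean change lies wholly above zero with no vaccine effect = 1 − Φ(1.96 − *f d* √*n*), by normal approximation.

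For *f* = *d* = 0.5 and *n* = 20: *f d* = 0.25, 0.25 × √20 = 1.118, and 1 − Φ(0.842) = 20%.

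| *n* | *f d* = 0 | *f* = 0.25, *d* = 0.25 | *f* = 0.5, *d* = 0.5 | *f* = 1, *d* = 1 |
|---|---|---|---|---|
| 20 | 2.5% | 4.6% | 20% | 99% |
| 30 | 2.5% | 5.3% | 28% | about 100% |
| 40 | 2.5% | 5.9% | 35% | about 100% |

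The values 20 and 30 are the planned limits for previously vaccinated women, and 40 is the maximum total. Across these assumptions the artefact runs from 0.06 to 1.0 SD, so the range settles nothing about the true size. With the same feeding state at both samples, *f d* = 0 and the nominal 2.5% returns.

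**Between groups.** If both groups eat alike, each mean change carries the same *f d*, and the difference between booster and first-dose participants carries *f d* − *f d* = 0.

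**The case against.** The strongest case against is that the consequence is thin. Laboratory output is descriptive, with no test, interval or decision rule attached to laboratory change, so the percentages above concern an interval that the protocol does not plan. The study-halt criteria in 10.2 rest on serious or severe adverse reactions, not on mean laboratory values. The primary objective compares booster with vaccine-naïve participants, and there the shift largely cancels. Change tables are also not the only view of laboratory effects: out-of-range results are presented separately, an investigator judges their clinical significance, and significant ones become adverse events. All of this stands, and it keeps the point minor.

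A reader might go further and infer that every post-dose sample is unfasted, so that the mean change is wrong by a full meal effect. The protocol does not support that. It says only that no fast is required. Some women will have gone hours without food in any case, and 4 hours is a short fast.

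A reader might also conclude that food will certainly raise the number of out-of-range flags. That depends on reference ranges held in a separate document that is not shown.

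What the objection leaves untouched is the mismatch itself. The protocol fixes both the Screening fast and the Screening baseline, and does not carry the fast forward.

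**Conclusion.** The point holds as a minor comparability flaw. Within-group change in glucose and triglycerides at Days 8, 29 and 57 can be biased because the baseline is fasted and the follow-up is not standardised. Upward is the likely direction, given that these two analytes tend to rise after a meal. Flags at these visits and at Day 183 may also be affected. The size cannot be derived from the documents.

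The conclusion rests on two conditions: that at least some post-dose samples are taken soon after eating, and that no other trial document restricts or records meals at those visits. It does not extend to the other 22 biochemistry tests, to haematology, or to the booster versus first-dose contrast where both groups eat alike.

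**What to change.** In 10.5.2.1, apply the same fasting instruction at Screening and at every visit with laboratory sampling: Days 8, 29, 57 and 183. This removes the bias at source. It costs a short fast before three more visits, or four with Day 183.

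If that is not done, record time since last meal at each laboratory visit. In the 10.9.4.3 tables, mark the glucose and triglyceride change rows as fasted baseline against non-standardised follow-up, not to be read as a vaccine effect. This costs one eCRF field and a footnote. For samples already drawn, the footnote may be all that remains possible.

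Removing the two analytes from the change tables would be the weaker remedy, since it discards planned safety output to cure a problem of interpretation.

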10.5.2.2 Fluid Intake

There are no fluids restrictions.

10.5.2.3 Alcohol Intake

Consumption of alcoholic beverages within 24 h prior and post dosing and scheduled clinic visits is not allowed.

Any deviation outside this alcohol intake restriction will be assessed on a case-by---case basis at Investigator's discretion (provided the participant's alcohol intake will not impact in the safety aspects and objectives of the study and the participant has a negative alcohol screen prior to dosing).

10.5.2.4 Caffeine

There are no caffeine restrictions during the study.

However, there are no caffeinated drinks available in the Clinical Unit.

10.5.2.5 Poppy and Sesame Seeds

Participants will be advised that they must not eat food containing poppy and/or sesame seeds for 3 days before each visit to the Clinical Unit, as consumption of poppy and/or sesame seeds can lead to a positive opiate result in the drugs of abuse test.

10.5.2.6 Grapefruit Juice and Other Restrictions

There are no restrictions on having food or drink containing grapefruit, cranberry, or Seville oranges.

10.5.3 Other Life-Style Restrictions

Participants are required to abstain from:

- Donation of blood or blood products for 90 days after dose of IMP.
- Use of cosmetics or creams at the site of vaccination that were known to cause irritation, within 24 h prior to dosing and for the duration of the study.
- Excessive exercise or a significant change in usual exercise habit within 7 days prior to dosing and for 7 days post-dosing.

10.5.4 Removal of Participants from Further Assessment

Each participant will be informed of their right to withdraw from the study at any time and for any reason.

An Investigator may withdraw participants from the study at any time for any of the following reasons:

- If a participant experiences a serious or intolerable AE, that prevents them from continuing. Participants will be followed-up for safety and until resolution of the AE unless lost to follow-up.
- If a participant incurs a significant protocol violation which impacts on their safety or the scientific integrity of the study.
- At the request of the Sponsor.
- If it is considered that the participant's health is compromised by remaining in the study or the participant is not sufficiently cooperative.
- If a participant is lost to follow-up.
- Pregnancy before Day 85 (will be discussed with the participant and sponsor to establish continuation of monitoring required).

All cases will be discussed on a case-by-case basis with the sponsor. The decision and the reason for any participant withdrawal will be recorded on the study completion form of the electronic case report form (eCRF).

If a participant is withdrawn or chooses to withdraw from the study for any reason every possible effort will be made to perform the evaluations described for the post-study follow-up (see Table 10.7.1). The data collected from withdrawn participants will be included in the study report.

In the event of any abnormalities considered to be clinically significant, participants will be followed-up with appropriate medical management until values are considered to be clinically acceptable. Referral or collaborative care will be organised if considered necessary.

A minimum of 30 and maximum of 40 female participants are required to complete the study. Participants who withdraw from the study before receiving any IMP will be replaced if suitable reserves are available. Participants who are withdrawn from the study due to significant drug-related AEs will not be replaced. Replacement of all other participants withdrawn from the study after receiving IMP will be decided on a case-by-case basis by the Principal Investigator (or deputy) and Sponsor.

10.6 Investigational Medicinal Product

10.6.1 Identity

The GBS-NN/NN2 vaccine will be supplied as a pre-mixed sterile solution for injection, comprising of 0.35 mg/mL of GBS-NN, 0.35 mg/mL of GBS-NN2 in 7 mM phosphate, 150 mM NaCl pH 7.2. The vial volume is 2.5 mL.

Alhydrogel will be supplied as a sterile suspension for injection containing Alhydrogel 0.5 mL at 1.4 mg/mL Al³⁺.

Active doses will be assembled by transferring 0.2 mL of GBS(NN+NN2) into a vial of Alhydrogel, inverting gently and then withdrawing 0.5 mL for injection.

The identity of each IMP is detailed in Table 10.6.1.

Table 10.6.1 Identity of Investigational Medicinal Products

| Product Name | Strength ¹ | Form |
|---|---------------------------------------|---|
| Pre-mixed vial containing 0.35 mg/mL each of GBS-NN and GBS-NN2 | 0.35 mg/mL each of GBS-NN and GBS-NN2 | Sterile solution for injection (2.5 mL) |
| Alhydrogel® | 1.4 mg/mL Al ³⁺ ion | Sterile suspension for injection (0.5 mL) |

10.6.2 Receipt and Storage

The IMP (pre-mixed vial containing 0.35 mg/mL each of GBS-NN and GBS-NN2) will be supplied by the Sponsor.

The Sponsor must notify the Principal Investigator, or the Project Manager, prior to dispatch of IMP supplies, and of the anticipated date of their arrival. IMP should arrive at the study site at least 7 days before the first dosing day. The Sponsor shall address all supplies to:

The Production Manager

IMP Management

Simbec-Orion

[name]

[name]

Upon receipt, supplies will be dealt with as per Simbec-Orion SOPs. Temperature monitors included with shipments will be downloaded.

On receipt at the Investigator site, IMPs will be stored under quarantine in a segregated, trial specific GMP area. Pre-mixed vial containing 0.35 mg/mL each of GBS-NN and GBS-NN2 will be stored at -20°C. Alhydrogel® will be stored at 2 to 8°C. A Simbec-Orion Qualified

Person (QP) will review the shipping documentation and bulk product QP certification. The supplies will be subsequently removed from quarantine and approved for use.

10.6.3 Assembly and Release

The IMP will be assembled into unit doses by suitably trained Simbec-Orion staff according to Simbec-Orion SOPs.

The IMP will be labelled as specified in Annex 13 (manufacture of IMPs) of the European Commission (EC) guide to Good Manufacturing Practice (GMP)^[255].

The finished IMP will be certified by a Simbec-Orion QP and stored in a secure, temperature-controlled GMP area according to Simbec-Orion SOPs.

10.6.4 Administration

The finished IMP (individual subject doses) will be presented in labelled syringes containing 0.5 mL for intramuscular administration with a 24-h expiry.

All participants will receive a 0.5 mL intramuscular injection of 50 µg GBS-NN/NN2 on Day 1.

Administration will be by intramuscular injection, preferably into the deltoid muscle of non-dominant arm. The dominant arm may be used if it is not possible to administer into the non-dominant arm e.g., due to a tattoo.

IMP administration, including the time and site, will be documented in the eCRF.

10.6.5 Return/Destruction

All used IMP containers and unused IMP will be held under quarantine pending return/destruction.

The Sponsor must provide approval for return/destruction of all remaining IMP within 8 weeks study completion. After this period, a charge for storage will be incurred.

All returns will be arranged at the earliest available delivery date. For IMP destruction, the Sponsor will receive the Certificate of Destruction 4 to 6 weeks from the date of removal from site.

10.6.6 Method of Assigning Participants to Treatment Groups

This is an open label study. All participants will receive a single intramuscular injection of GBS-NN/NN2 containing 50 µg of GBS-NN and 50 µg of GBS/NN2.

Participants will be numbered sequentially from 001 (i.e., 001, 002 etc.). Replacement participants will be assigned the same number as the participant they are replacing, however, 100 will be added to the number (i.e., 101 would replace 001 etc.).

10.6.7 Selection of Doses in the Study

The dose selected is based on safety and Pharmacodynamic (PD) data from MVX0002 study.

10.6.8 Timing of Dose for Each Participant

Doses will be administered after all pre-dose assessments have been completed.

10.6.9 Blinding

Not applicable, all participants will receive a single dose of GBS-NN/NN2 containing 50 μ g of each fusion protein.

10.6.10 Prior and Concomitant Therapy

10.6.10.1 Prior Medication:

Prescription or non-prescription drugs, including vitamins, herbal and dietary supplements should not be taken within 28 days (or 5 half-lives (whichever is longer)) prior to the first dose of IMP with the exception of contraceptives and paracetamol (which may be taken as an analgesic to a maximum of 2 g in 24 h). If applicable this will be noted in the participant's eCRF.

The use of prior medication is not permitted for any vaccine naïve participants i.e., those who did not participate in the MVX0002 study or for individuals who participated in the MVX0002 study (both active and placebo) who have not developed new medical conditions which require the use of chronic medications considered as permitted as detailed below.

If participants who participated in the MVX0002 study (either active or placebo recipients) have developed new medical conditions which require the use of chronic medications that do not affect the immune system, the inclusion of such participants will be permitted at the discretion of the Investigator on a case-by-case basis and only if it is considered that the inclusion within the MVX0003 study will not be detrimental to participant safety. Any use of prior medication in this circumstance will be noted in the participant's eCRF.

